### Statistical Analysis—Specific Aim 1 Primary Outcome.

We will test the primary hypothesis that among Veterans with overweight or obesity, MOVE!+UP will result in significantly greater weight loss using linear mixed effects models. Because this is an RCT, no imbalance across conditions is anticipated. To increase precision of outcome effect estimates, the analysis will adjust for baseline weight and an indicator of self-reported African-American status. Participants in the same enrollment cohort who are assigned to the same treatment arm receive group treatments together, so their outcomes are correlated. To account for this, we will include a random intercept for group treatment cluster in the model. The primary analysis will be based on the following model:

$$Y_{ij}^{(6)} - Y_{ij}^{(0)} = \beta_0 + \beta_1 Intervention_i + \beta_2 Y_{ij}^{(0)} + \beta_4 x_i + \tau_j + \varepsilon_{ij}$$

Where:

- $Y_{ij}^{(6)} - Y_{ij}^{(0)}$  is the *difference in weight at 6 months* ( $Y_{ij}^{(6)}$ ) and baseline ( $Y_{ij}^{(0)}$ ) for subject  $i$  in group treatment cluster  $j$ ;
- $Intervention_i$  is an indicator of assignment to the intervention MOVE!+UP;
- $Y_{ij}^{(0)}$  is baseline weight;
- $x_i$  are baseline covariates; and
- $\tau_j$  is the random intercept for group treatment cluster  $j$ .

Our main goal is to test whether  $\beta_1=0$ , which is the difference in weight change between intervention and control groups. A strength of our approach includes accounting for correlated responses among intervention participants in the same treatment cluster. The approach we chose assumes a homogenous variance between the clusters (cohorts); a recent study showed this may be acceptable in scenarios where ICCs are low, as assumed in our study. Our approach of adjusting for baseline weight and pre-specified baseline covariates will provide the most efficient way of estimating the effect of intervention.

We will calculate a point estimate and 95% confidence interval for the effect of intervention,  $\beta_1$ , based on the fitted mixed effects model. A test of the null hypothesis of no intervention effect,  $\beta_1=0$ , will be conducted using a significance threshold of 0.05. The test will be based on a t-statistic with denominator degrees of freedom calculated using the Kenward-Rogers approximation. Since we are only testing a single hypothesis for the primary analysis, no adjustment for multiplicity will be needed.

### Aim 1 Secondary and Aim 2 Exploratory Analyses

We will compare intervention and control conditions on 6-month PTSD symptom reduction, 12-month weight loss and PTSD symptom reduction, and 6-month change from baseline for other treatment targets. The primary outcome model will be used for continuous outcomes. Note that

only the weight models will include African-American race as a covariate. Binge eating disorder at 6 months will be analyzed using a random intercept logistic regression model with an indicator variable for intervention arm. We will use the same statistical test as described for the primary analysis. Given analyses are exploratory, no adjustment for multiple comparisons will be made.

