### 3.0 Objectives

Posttraumatic Stress Disorder (PTSD) is common among Veterans and results in poor psychological functioning, quality of life, and physical health. This includes having disproportionately high rates of obesity, in part due to PTSD symptoms interfering with physical activity and healthy diet. Unfortunately, Veterans with PTSD have poorer weight loss outcomes than those without PTSD in VA’s existing weight management program, *MOVE!*. Based on pilot work, it appears that *MOVE!+UP*, a weight management program that augments standard PTSD care and targets PTSD-related barriers to weight loss, improves weight and PTSD symptoms. Whether it improves these issues more than standard VA care is in need of study, which is the focus of the proposed research. The proposed study also seeks to understand factors that would interfere with and facilitate implementing the program in VA if it is effective.

We expected to enroll approximately 164 overweight or obese Veterans with PTSD who are currently receiving PTSD care at VA Puget Sound into this hybrid type 1 randomized controlled trial. We enrolled an additional 15 participants (a total of 179) to ensure adequate participants in the final cohort to have robust groups and to ensure 164 Veterans were randomized, per primary analysis power calculations. Participating in the study took a total of a year. Assessment visits were held when participants first enroll and 6 months after enrolling in the study. A final weight and PTSD symptomology assessment was done one year after enrollment. A questionnaire was also mailed to all participants at 16 weeks to assess satisfaction with the weight management program they participated in. The study aims were as follows:

**Aim 1:** Among overweight or obese Veterans with PTSD enrolled in PTSD care, test whether intervention participants have greater 6-month weight loss (primary outcome), and 6-month PTSD symptom reduction and 12-month weight loss and PTSD symptom reduction (secondary outcomes), relative to controls.

**Aim 2:** Assess whether compared to control, intervention participants have greater improvements on 6-month treatment targets: physical activity, eating behavior, insomnia, depression, and social support.

**Aim 3:** Estimate intervention and control condition costs and utilization, and identify MOVE!+UP implementation barriers and facilitators, to contextualize Aim 1 and inform future implementation.

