**Table 5. Quantitative Measures for RCT: Covariates, and Aim 1 and 2 Outcomes**

Domain	Measure
Baseline Covariates Associated with Weight or PTSD (will be adjusted in a weight or b PTSD analyses)	
African-American race/ethnicity a	Self-reported African-American race/ethnicity 
Aim 1: Test MOVE!+UP's Effects on Weight (Primary) and PTSD (Secondary) Outcomes	
Primary outcome: weight loss	Standardized protocol and equipment at baseline and 6 months. Will also explore 12-month weight loss in secondary analyses.
Secondary outcome: PTSD symptoms	PTSD Checklist for DSM-5  PTSD symptomology will be recorded at baseline, 6 months, and 12 months.
Aim 2: Exploratory Changes on Treatment Targets from Baseline to 6 months	
Diet quality and eating habits	Starting the Conversation  and PACE eating habits measure
Night eating	Night Eating Questionnaire 
Emotional eating	Emotional Overeating Questionnaire 
Binge eating with purging vs binge eating without purging vs no binge eating	PHQ-15  modified to reflect DSM-5 changes plus items from PACE eating habits
Two outcomes: Average physical activity (light, moderate, and vigorous; moderate and vigorous)	Actigraph accelerometers, gold standard 
Social support	Helpful and unhelpful behaviors from others for activity/diet 
Insomnia severity	Insomnia Severity Index 
Depression symptoms	PHQ-8 
Internalized Weight Bias	Modified Weight Bias Internalization Scale

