**Note: Aim 3 analyses are not covered in this statistical analysis plan.**

Table 1. Statistical Models

Analysis	Outcome(s)	Independent Variables
Primary analysis	6-month absolute weight change from baseline (pounds)	Binary treatment indicator  Baseline weight  Binary African-American race indicator
Secondary analyses	1. 6-month absolute change in PTSD symptoms from baseline 2. 12-month absolute change in PTSD symptoms from baseline 3. 12-month absolute weight change from baseline (pounds)	Binary treatment indicator  Baseline outcome  Binary African-American indicator (weight analysis only)
Exploratory analyses	6-month absolute change from baseline in: 
 
Diet quality
 
Eating habits
 
Night eating
 
Emotional eating
 
Average MVPA and average LMVPA (adjust for total # of valid days at baseline and 6 months)
 
Social support – Diet
 
Social discouragement – Diet
 
Social support – physical activity
 
Social discouragement – physical activity
 
Insomnia Severity Index (ISI)
 
Depression symptoms
 
Internalized Weight Bias
 
	Binary treatment indicator  Baseline outcome

 All models account for clustering through the inclusion of a random intercept for group treatment cluster.

Analysis	Outcome(s)	Independent Variables
Exploratory Analyses	Binge eating at 6 months	Binary treatment indicator
Sensitivity analyses:  adjusting for prior weight loss treatment	1. 6-month absolute weight change from baseline (pounds) 2. 12-month absolute weight change from baseline (pounds)	Binary treatment indicator  Baseline outcome  Binary African-American indicator  Total number of MOVE! visits 12 months prior to baseline  Binary indicator of prescription weight loss medications at baseline
Sensitivity analyses:  adjusting for prior mental health treatment	1. 6-month absolute change in PTSD symptoms from baseline 2. 12-month absolute change in PTSD symptoms from baseline	Binary treatment indicator  Baseline outcome  Total number of mental health visits 12 months prior to baseline, per EHR  Number of PTSD visits in the prior year  Binary indicator of PTSD medications in the last year

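### Binge eating at 6 months is the only Aim 2 outcome modelled without its baseline value: the test is valid, but the odds ratio is pulled toward 1 and some power is given up

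*Combined protocol and SAP*

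**What the plan says.** In Section 5.6.b, under Aim 1 Secondary and Aim 2 Exploratory Analyses: "Binge eating disorder at 6 months will be analyzed using a random intercept logistic regression model with an indicator variable for intervention arm". In Table 1 (Statistical Models) the row "Binge eating at 6 months" lists only the treatment indicator. The 12 other exploratory items list the treatment indicator and the baseline outcome, in line with "The primary outcome model will be used for continuous outcomes". The primary analysis section gives the plan's reason for baseline adjustment: "To increase precision of outcome effect estimates, the analysis will adjust for baseline weight", together with race.

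Aim 2 (Section 3.0) asks whether, relative to control, "intervention participants have greater improvements on 6-month treatment targets". Table 5 places binge eating among changes from baseline to 6 months and records it as "Binge eating with purging vs binge eating without purging vs no binge eating".

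On the test, the sentence directly after the logistic model reads "We will use the same statistical test as described for the primary analysis". That test is a t-statistic with "denominator degrees of freedom calculated using the Kenward-Rogers approximation".

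Section 5.5 says that the exploratory questionnaire was administered by staff before randomization from cohort 2 onward, that some baseline questionnaires were lost before then, and that the 6-month assessment mirrors baseline. The Missing data text commits to multiple imputation for primary and secondary outcomes only.

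**The concern.** The plan treats baseline adjustment as its standard tool and drops it, without explanation, for the one binary outcome. If binge eating persists in individuals, baseline status carries much of the information about 6-month status. An arm-only model then discards power on an outcome with few events, and a chance difference at baseline shows up in the reported odds ratio.

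Two further details are left open. The stated test is written for a linear mixed model, and no estimation method is named for the logistic one. The outcome is also not pinned down: Table 5 has three categories, the model needs two, and the text refers to the disorder while Table 1 refers to the behavior. Two analysts could follow the plan and report different results.

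**Working it through.** **The plan's own figure.** The documents give no power or effect size for binge eating. The only relevant figure is the overall sample size (Section 5.6.b and Table 7: difference 8.4 lb, SD 13, two-sided alpha 0.05, power 90%, ICC 0.03, cluster size 8, attrition 25%).
- Per arm, unclustered: 2 × (13 × (1.960 + 1.282) / 8.4)² = 50.33
- Design effect: 1 + (8 − 1) × 0.03 = 1.21, giving 60.9
- Attrition: 60.9 / 0.75 = 81.2, rounded up to 82 per arm, 164 in total

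This reproduces the plan. Expected completers are 82 × 0.75 = 61.5, taken as 62 per arm.

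**Assumptions for the power check (not in the documents).** Prevalence of 25% or 15%, used both at baseline and for the control arm at 6 months. The 25% is the pilot cohort 5 baseline rate; with n = 8 (2 of 8) its exact 95% interval runs from 3% to 65%, so it is only a rough anchor. The odds ratio linking baseline to 6-month status is 1, 5, 10 or 20. The treatment odds ratio, given baseline, is 0.3. Model: logit P(binge at 6 months) = a + log(baseline OR) × baseline + log(treatment OR) × arm. There were 3,000 simulated trials per setting, analyzed by logistic regression with and without baseline, Wald test at 0.05. The cluster random intercept was omitted.

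| Prevalence | Baseline OR | Power, arm only | Power, with baseline | Difference (points) |
|---|---|---|---|---|
| 25% | 1 | 65.4% | 64.6% | −0.8 |
| 25% | 5 | 60.1% | 63.6% | 3.5 |
| 25% | 10 | 51.2% | 59.3% | 8.1 |
| 25% | 20 | 40.4% | 53.4% | 13.0 |
| 15% | 1 | 38.2% | 39.1% | 0.9 |
| 15% | 5 | 34.4% | 37.2% | 2.8 |
| 15% | 10 | 32.4% | 37.6% | 5.2 |
| 15% | 20 | 27.7% | 35.1% | 7.4 |

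Simulation error on each power is at most √(0.25/3000) = 0.9 points. With a treatment odds ratio of 1, rejection rates were 3.6% to 5.0% for both models. Non-estimable runs were excluded; at 15% prevalence they reached 517 of 3,000 (17%).

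**Where the gain comes from.** At 25% prevalence and baseline odds ratio 10, the median log odds ratio moves from −1.00 to −1.24, while its standard error rises from 0.50 to 0.58. The ratio goes from 1.00/0.50 = 2.0 to 1.24/0.58 = 2.1. The adjusted estimate is less precise on the log-odds scale but further from zero.

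**A second scenario.** Assume 130 completers (174 randomized × 0.75 = 130.5), 25% baseline prevalence, and 6-month rates of 55% with and 6% without baseline binge eating. The implied baseline odds ratio is (0.55/0.45)/(0.06/0.94) = 19, the strong end of the range. Power goes from 31% to 38% for a treatment odds ratio of 0.35, and from 46% to 57% for 0.25. With a baseline odds ratio of 4.9 and a treatment odds ratio of 0.35, it goes only from 43% to 45%.

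**Chance imbalance, same assumptions, no treatment effect.** Let 13 of 65 controls and 20 of 65 intervention participants have baseline binge eating. Expected 6-month rates are (13 × 0.55 + 52 × 0.06)/65 = 15.8% and (20 × 0.55 + 45 × 0.06)/65 = 21.1%, an unadjusted odds ratio of about 1.4. In simulation the median was 1.41 unadjusted and 0.97 adjusted. An imbalance at least this large, in either direction, occurs in about 19% of trials.

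**The reference distribution.** 164/8 gives about 20 clusters. With roughly 18 degrees of freedom the critical value is 2.10, against 1.96 for a large-sample Wald test: a modest but real difference.

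**The case against.** The arms are randomized, so comparing 6-month status by arm is a valid test of whether the intervention improves binge eating. Chance imbalance is already covered by its error rate, which stayed near or below 5%. That stands. A reader might infer that the model fails to answer Aim 2, but the documents do not support that; the issue is efficiency.

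A reader might also infer that precision is lost. That is wrong for a logistic odds ratio: adjustment raises the standard error. What is lost is power, because the arm-only odds ratio is a different, attenuated quantity.

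Nor can one say that the stated test cannot apply. Kenward-Roger is not defined for a logistic mixed model fitted by maximum likelihood, but it can be used with a pseudo-likelihood (linearized) fit, and the plan names no method. The sentence could also be meant only for the continuous outcomes, or only as a test of the arm coefficient at 0.05. This is missing detail, not a demonstrated error.

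On size, nothing in the documents shows how far binge eating persists. Pilot cohort 5, falling from 25% to 0%, says nothing about it. The large gains need a very strong association. With about 18 events expected in the second scenario (treatment odds ratio 0.35), a sparse model is defensible. Adjustment is also not free: some baseline questionnaires were lost and no imputation is promised for Aim 2. If 10% of baseline values were missing and those participants dropped (an assumed figure), the gain in the second scenario would shrink to about 2 to 4 points.

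These arguments limit the size of the point and shape the remedy. They do not explain why this outcome alone goes unadjusted.

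**Conclusion.** The point holds as an unexplained inconsistency with a modest cost in power. The arm-only test is valid. Its odds ratio is attenuated when baseline status predicts 6-month status, and power is lower by about 0 to 13 percentage points over baseline odds ratios of 1 to 20 and prevalences of 15% and 25%. Those inputs are assumptions, and the simulation ignores clustering. The missing estimation method, the test carried over from the linear model and the undefined binary outcome are secondary clarifications. Severity is minor.

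**What to change.** 1. Add baseline binge eating (yes/no) to the logistic model in the text and to its row in Table 1 (Statistical Models).
2. State a rule that keeps participants whose baseline questionnaire was lost, for example by including this outcome and its baseline value in the multiple imputation. Without such a rule most of the gain could disappear.
3. State a fallback for sparse cells or separation, such as Firth-penalized logistic regression, and say how clustering is handled if the fallback is used.
4. Name the estimation method and a test that matches it and allows for the small number of clusters. If Kenward-Roger is intended, say that the fit is pseudo-likelihood.
5. State how Table 5's three categories become the binary outcome, and use one label for it in the text and in Table 1.

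The cost is a few sentences in the SAP, one covariate in a model with few events, and the missing-baseline rule. No new data are needed, and the primary analysis and sample size do not change.

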**Note: Aim 3 analyses are not covered in this statistical analysis plan.**

Table 1. Statistical Models

Analysis	Outcome(s)	Independent Variables
Primary analysis	6-month absolute weight change from baseline (pounds)	Binary treatment indicator  Baseline weight  Binary African-American race indicator
Secondary analyses	1. 6-month absolute change in PTSD symptoms from baseline 2. 12-month absolute change in PTSD symptoms from baseline 3. 12-month absolute weight change from baseline (pounds)	Binary treatment indicator  Baseline outcome  Binary African-American indicator (weight analysis only)
Exploratory analyses	6-month absolute change from baseline in: 
 
Diet quality
 
Eating habits
 
Night eating
 
Emotional eating
 
Average MVPA and average LMVPA (adjust for total # of valid days at baseline and 6 months)
 
Social support – Diet
 
Social discouragement – Diet
 
Social support – physical activity
 
Social discouragement – physical activity
 
Insomnia Severity Index (ISI)
 
Depression symptoms
 
Internalized Weight Bias
 
	Binary treatment indicator  Baseline outcome

 All models account for clustering through the inclusion of a random intercept for group treatment cluster.

Analysis	Outcome(s)	Independent Variables
Exploratory Analyses	Binge eating at 6 months	Binary treatment indicator
Sensitivity analyses:  adjusting for prior weight loss treatment	1. 6-month absolute weight change from baseline (pounds) 2. 12-month absolute weight change from baseline (pounds)	Binary treatment indicator  Baseline outcome  Binary African-American indicator  Total number of MOVE! visits 12 months prior to baseline  Binary indicator of prescription weight loss medications at baseline
Sensitivity analyses:  adjusting for prior mental health treatment	1. 6-month absolute change in PTSD symptoms from baseline 2. 12-month absolute change in PTSD symptoms from baseline	Binary treatment indicator  Baseline outcome  Total number of mental health visits 12 months prior to baseline, per EHR  Number of PTSD visits in the prior year  Binary indicator of PTSD medications in the last year
Sensitivity analyses:  Including auxiliary variables to assess impact of missing data	1. 6-month absolute weight change from baseline (pounds) 2.	Binary treatment indicator  Baseline outcome  Binary African-American indicator (weight analyses only)  Auxiliary variables discussed in the Handling of Missing Data section. Plus those that appeared possibly associated with missingness on 6-month weight in descriptive comparisons.
Sensitivity: bariatric surgery	1. 6-month absolute weight change from baseline (pounds) 2. 12-month absolute weight change	Binary treatment indicator

Analysis	Outcome(s)	Independent Variables
influence	from baseline (pounds)	
Baseline outcome
 
Binary African-American indicator (weight analyses only)
 
Remove veteran outcome with bariatric surgery. However no one had bariatric surgery during the study period so this analysis is not being conducted.

Sensitivity analysis: examine differences in utilization across tx conditions and the influence of these factors on weight loss outcome.	
 
1. 6-month absolute weight change from baseline (pounds)
 
2. 12-month absolute weight change from baseline (pounds)
 
3.
 
	
Binary treatment indicator
 
Baseline outcome
 
Binary African-American indicator (weight analyses only)
 
-Binary indicator of prescription weight loss medications from baseline to 6 and 12 months reported in EHR and/or self report
 
-binary indicator of non-MOVE! +UP/MOVE! weight management care (i.e., any self-reported non-Va program, dietician visits TeleMOVE!). Will not include self-reported use of websites, Fitbits etc.
 
If the pattern of results changes from what was found in the primary analysis, we would pursue a formal mediation analysis.

Sensitivity analysis: If we see substantial issues with the q-q plots when the primary analysis is	
 
1. 6-month log-transformed weight change from baseline (pounds)
 
1.
 
	
Binary treatment indicator
 
Baseline outcome
 
Binary African-American indicator (weight analyses only)

Analysis	Outcome(s)	Independent Variables
run, we will do a sensitivity analysis with a log-transformed outcome		

**Qualitative Data Coding and Analysis—Aim 3.** If we have a positive trial, we will use template analysis, a method for thematic coding of text well suited when the aim is to investigate themes with a clear structure. The CFIR will guide coding and analysis of qualitative interview transcripts, field notes, and suggestions on Veteran satisfaction measures, using CFIR coding guidelines. Coding discrepancies will be resolved by a consensus approach with input from our co-investigators. After codes have been applied to each data source, memos will be written with summary statements and corresponding supporting quotes. Findings will be summarized in products and will guide adaptations to *MOVE!+UP* content and procedures, and inform future implementation activities.

5.7    **Withdrawal of Subjects**

a. Veteran participants (Aims 1 and 2)  
 Participants were reminded that they are free to withdraw from the study at any time without loss of any materials they have obtained through the study and that their information will be kept confidential. If an immediate and serious risk is discovered, staff will consult with the PI, [name].

If the data and safety monitoring committee (DSMC) member(s) determine that involvement in the study was not in a Veteran's best interest, we would withdraw them from the study. Although we did not identify hard-and-fast stopping rules because we wanted to make Veteran involvement as individualized as possible, we would likely withdraw a participant from the study if they expressed suicidal intent or had an extreme exacerbation of PTSD symptoms (i.e., an increase of 10 points on the PTSD Checklist in the course of a week) that they and/or PI or DSMC attributed to study participation. Any adverse effect of moderate or greater severity deemed to be definitely associated with the study will be reported to the participant and his/her health care provider(s). Serious adverse events (SAEs) will be reported to the IRB following standard IRB requirements. We will consult the DSMC to assess the impact of significant data loss due to problems in recruitment, retention or data collection.

Should something come up that may affect the subject's health or welfare (for example a subject becomes pregnant or plans bariatric surgery during the study)

we would require that subject speak with their primary care provider or other physician to confirm that it is okay for them to continue participating in the study.

If a participant decided to withdraw, or if they were terminated from the study, a person from the study team may need to meet with them to discuss the necessary steps that they may need to take to end Veteran participation in the study. Veterans were also reminded that If they decided to withdraw from the study, no new information would be collected from them (aside from prospective CDW data, noted in the consent as described above); however, data already collected will continue to be part of the analyses.

b. VA Employees (Aim 3)

VA staff participants will be assured that they can, at any time, refuse to answer any question, and at any time elect to withdraw from the study. They also will be assured that their participation or lack thereof will not be reported to their supervisor or peers nor will it have any impact on their work environment and that they are free to participate in the presence of union representation.

